## 1. Study Protocol

In this study, a double-blind randomized experimental design was used to allow subjects to take six months of health supplements (experimental group) and six months of placebo (control group) to see their effects on fatty liver, liver fibrosis and metabolic indicators.

First ask the patient to agree to participate in the trial and fully understand the content of the project. After the eligible subjects are evaluated and confirmed to be able to participate in the trial, they will take health care products daily according to the research setting (3 tablets before breakfast, 3 tablets before dinner, total 6 tablets ), at the first time of the test, 4 weeks, 8 weeks, 12 weeks, 16 weeks, and 24 weeks respectively to check blood and biochemical values, including creatinine (Cr), liver function index (AST, ALT), pre-meal blood sugar (AC) , And use Fibroscan to detect fatty liver and liver fibrosis. At the first time of the test, 4 weeks, 12 weeks, 12 weeks, 12 weeks, and 24 weeks, return to check blood routine / white blood cell classification examination (CBC/DC), uric acid (UA), cholesterol blood fat (HDL, LDL), triglyceride (TG), lipid Adiponectin/Leptin (Adiponectin/Leptin), C-reactive protein (CRP), insulin (Insulin); In addition, at the first, 12 weeks, and 24 weeks of the test, the metabolic indicators related to glycosylated hemoglobin (HbA1c) were tested.

This study will extract the follow-up data of subjects' return visits for analysis and research. The follow-up methods are phone reminders two weeks before the start of the trial, and reminders during monthly visits, asking about taking status, etc., to increase the subjects' compliance.

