#### SCHEDULE OF EVENTS

## 3. Statistical Analysis Plan

This study is expected to include a total of 60 people with non-alcoholic fatty liver disease, divided into two groups, 30 people in each group, double-blind randomized test. The primary end point (primary end point) is to see the severity of changes in the patient's steatohepatitis and fibrosis. The secondary end point is the degree of change in the patient's weight and lipid profile. Continuous variables are presented in normal probability plots and Shapiro-Wilk test evaluation. The relationship between variables Connectivity is analyzed by Pearson's correlation, and the Intra-intervention comparison is performed by Paired t test. Unify The calculation software is based on R software version 2.11.1.

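### The metabolic aim reaches the end points only through weight and lipids; HbA1c and six other measured markers have no tier, so any of them could be used to claim that aim.

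*Combined protocol and SAP*

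**What the plan says.** Section 1 (Study Protocol) describes a six-month comparison of a supplement with placebo to see "their effects on fatty liver, liver fibrosis and metabolic indicators". The term for the third part of the aim is not defined. It appears once more in that section, where the visit list reaches HbA1c: "the metabolic indicators related to glycosylated hemoglobin (HbA1c) were tested".

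Section 1 also lists "pre-meal blood sugar (AC" among the tests done at every visit, and a second panel that includes "uric acid (UA), cholesterol blood fat (HDL, LDL), triglyceride (TG), lipid Adiponectin/Leptin (Adiponectin/Leptin), C-reactive protein (CRP), insulin (Insulin". The schedule in Section 2 places AC at First Time and weeks 4, 8, 12, 16 and 24. It places the second panel at First Time and weeks 4, 12 and 24, and HbA1c at First Time and weeks 12 and 24.

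Section 3 (Statistical Analysis Plan) says that the primary end point "is to see the severity of changes in the patient's steatohepatitis and fibrosis". It continues: "The secondary end point is the degree of change in the patient's weight and lipid profile". No exploratory tier, alpha, analysis visit or multiplicity rule is given. The only comparison named is this: "the Intra-intervention comparison is performed by Paired t test".

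**The concern.** Metabolic effect is one of three things the trial says it will study, yet the one marker that the protocol itself calls a metabolic indicator is in neither end-point tier. Nor are six other markers that a reader would naturally count as metabolic. The plan does not call them exploratory and does not say which of them would count towards the aim.

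A report could therefore state that the product improves metabolic indicators on the strength of whichever marker reached significance, and a reader could not tell a planned result from a selected one. The named test adds to the problem. A change from baseline within one arm does not show an effect against placebo, although the trial is randomised and placebo-controlled.

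**Working it through.** **The plan's own figure.** Section 3 gives 60 people, "divided into two groups, 30 people in each group, double-blind randomized test": 2 × 30 = 60, which agrees. It cannot be derived further, because no alpha, power, effect size or SD is given.

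**Which markers have no tier.** Items measured, from Sections 1 and 2: Cr, AST, ALT, AC, CBC/DC, UA, HDL, LDL, TG, adiponectin, leptin, CRP, insulin, HbA1c and FibroScan. Set aside:

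- FibroScan (primary end point);
- HDL, LDL and TG (lipid profile, secondary end point);
- AST and ALT (described as liver function);
- Cr and CBC/DC (renal function and blood count, not metabolic on the usual reading).

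Seven remain: HbA1c, AC, insulin, adiponectin, leptin, CRP and UA.

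**Chance of at least one false positive at week 24.** All seven are measured at week 24. Assume each is tested once there at two-sided 0.05, with no true effect on any.

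- One pre-named marker: 5%.
- Seven independent tests: 1 − 0.95^7 = 1 − 0.698 = 0.302, or 30%.
- Seven correlated tests, from a simulation of 400,000 sets of seven equally correlated normal test statistics with critical value 1.96:

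| Between-marker correlation | At least one of seven significant |
|---|---|
| 0 | 30% |
| 0.3 | 27% |
| 0.5 | 23% |
| 0.8 | 15% |

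The documents give no correlations, so the range is the result, not any single row.

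**Sensitivity to the other assumptions (independent tests).**

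- Adiponectin and leptin counted as one marker, 6 tests: 1 − 0.95^6 = 26.5%.
- AST, ALT, Cr and CBC/DC added as four items, 11 tests: 1 − 0.95^11 = 43.1%.
- Alpha of 0.01 instead of 0.05, 7 tests: 1 − 0.99^7 = 6.8%, against 1% for one marker.

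**What a false positive means here.** For a between-arm test it is a spurious difference from placebo. For the paired t test named in Section 3 it is a spurious change from baseline in one arm. Even a true change from baseline could occur in both arms, through regression to the mean or trial participation, so the within-arm test would not answer the question at any error rate.

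**The case against.** The strongest reply is that nothing is contradicted. The term for the third part of the aim is undefined, weight and lipids can fairly be read as metabolic, and an end point narrower than a general aim is ordinary. So is measuring a marker without giving it a tier. This stands in part. A reader might infer that the metabolic aim has no end point at all, or that aims and end points conflict outright; the documents do not support that, because the secondary end point covers part of the aim. What it leaves uncovered is the glycaemic, insulin, adipokine, CRP and uric acid markers.

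A second reply is that the HbA1c wording is loosely translated text in a visit list and does not show that HbA1c was meant to represent the aim. That is fair. The label makes HbA1c a natural choice; it does not prove intent.

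A reader might also infer that the paired t test will be run on every marker at every visit. The schedule would then give AC 5 + five markers × 3 + HbA1c 2 = 22 tests per arm, and 1 − 0.95^22 = 67.6% if all were independent. Repeated visits are correlated, so the true figure would be lower. More importantly, Section 3 names no marker and no visit for that test. The plan leaves such testing open without saying that it will be done, so this figure does not measure the plan as written.

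Finally, the gap leaves room for selective claiming. Nothing in the documents shows that this was intended or has occurred.

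**Conclusion.** The point holds in a limited form. One of three stated aims is tied to an end point only in part: seven measured markers have no tier, and nothing restricts which marker or visit may support a metabolic claim. At one visit, the chance of at least one falsely significant marker is about 15% to 30%, against 5% for a single pre-named one. This rests on an assumed two-sided 0.05, a count of seven markers, and between-marker correlation from 0.8 to 0. Testing at further visits would raise it.

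The primary end point is not affected by this gap in tiers. It should be corrected because it changes what the trial may conclude about metabolic effect.

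**What to change.** In Section 3, before unblinding:

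1. Name one metabolic secondary end point at one visit. HbA1c at week 24 is the natural choice, because the protocol gives it that label and already collects it at First Time, week 12 and week 24. Another marker would also close the gap if it is named in advance with a reason.
2. Analyse it as the between-arm difference at week 24 adjusted for baseline HbA1c, instead of by within-arm paired t tests.
3. Label AC, insulin, adiponectin, leptin, CRP and UA exploratory. Report them as between-arm estimates with 95% CIs, not as confirmatory evidence for the metabolic aim.

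The cost is SAP wording only, with no added visits, samples or participants. The downside is that a significant result on an exploratory marker can no longer be presented as meeting the metabolic aim.

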## 2. Study procedures

Evaluation Procedure	Regist ration	First Time	Week 4	Week 8	Week 12	Week 16	Week 24
Informed Consent	v	Α					
		B		2.		25	
Assess Eligibility	v	Α	8	5		2	
		B					
Blood inspect							
Cr 、 AST 、 ALT 、 AC CBC/DC 、 UA 、 HDL 、 LDL 、 TG 、 Adiponectin /leptin 、 CRP 、 Insulin		Α	Α	Α	Α	Α	Α
		B	В	В	В	В	В
		A	А		А		А
		В	В		В		В
HbA1c		Α			Α	-	Α
		В		5	B	2	В
FibroScan		Α	Α	Α	Α	Α	Α
		B	В	В	В	В	В

#### SCHEDULE OF EVENTS

## 3. Statistical Analysis Plan

This study is expected to include a total of 60 people with non-alcoholic fatty liver disease, divided into two groups, 30 people in each group, double-blind randomized test. The primary end point (primary end point) is to see the severity of changes in the patient's steatohepatitis and fibrosis. The secondary end point is the degree of change in the patient's weight and lipid profile. Continuous variables are presented in normal probability plots and Shapiro-Wilk test evaluation. The relationship between variables Connectivity is analyzed by Pearson's correlation, and the Intra-intervention comparison is performed by Paired t test. Unify The calculation software is based on R software version 2.11.1.

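### The analysis plan contains no comparison of supplement with placebo; its only test of change is a within-group paired t test

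*Combined protocol and SAP*

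**What the plan says.** Section 1 (Study Protocol) describes a double-blind randomized trial in which subjects "take six months of health supplements (experimental group) and six months of placebo (control group"), with the aim "to see their effects on fatty liver, liver fibrosis and metabolic indicators". Section 3 (Statistical Analysis Plan) says the 60 people are "divided into two groups, 30 people in each group, double-blind randomized test".

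Section 3 defines the outcome in one sentence: "The primary end point (primary end point) is to see the severity of changes in the patient's steatohepatitis and fibrosis". It names these analyses and no others:

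- normal probability plots and the Shapiro-Wilk test for continuous variables;
- for associations, "The relationship between variables Connectivity is analyzed by Pearson's correlation";
- for change, "the Intra-intervention comparison is performed by Paired t test".

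On measurement, section 1 says the trial will "use Fibroscan to detect fatty liver and liver fibrosis". Sections 1 and 2 schedule FibroScan at the first visit and at weeks 4, 8, 12, 16 and 24. No FibroScan reading is named, no visit is designated primary, and no rule says how the two components combine. The documents give no alpha, sidedness, power, effect size, SD or dropout rate.

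**The concern.** A placebo arm is there so that change on supplement can be judged against change without it. A paired t test within one arm asks only whether that arm's mean change differs from zero. Placebo response, regression to the mean and the attention that comes with regular visits can all move both arms. Under this plan, such movement would count in the supplement's favour. Setting the two within-arm p-values side by side does not help, because one arm being significant and the other not is not a test of the difference between them.

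A smaller matter concerns the end point itself. Section 3 says steatohepatitis where section 1 says fatty liver, and the reading, visit and success rule are left open. Even a correctly chosen between-arm test could then be applied to a reading or visit picked after the results are seen.

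**Working it through.** **No planned figure to reproduce.** The documents give 60 in total and 30 per group without any basis, so the sample size cannot be re-derived. Everything below takes n = 30 per arm from section 3. Assumptions are two-sided alpha 0.05, no dropout, normally distributed changes, and 80% power where power is used. Effects are in units of the SD of change.

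**1. Within-arm test when the supplement does nothing.** Let both arms have the same true mean improvement d. The paired t statistic is noncentral t with 29 degrees of freedom and noncentrality d × √30. The critical value is 2.045. Let p be the probability of a significant improvement in one arm. The arms are independent, so significance in the supplement arm only has probability p(1 − p).

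| d (assumed) | d × √30 | p, supplement arm significant | p(1 − p), supplement arm only |
|---|---|---|---|
| 0.2 | 1.095 | 0.184 | 0.150 |
| 0.3 | 1.643 | 0.355 | 0.229 |
| 0.36 | 1.972 | 0.479 | 0.250 |
| 0.5 | 2.739 | 0.754 | 0.186 |

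The last column cannot exceed 0.25, which is reached when p = 0.5. A two-sample t test on change rejects in 5% of trials at every d, because the shared change cancels.

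**2. Detectable effect, 80% power.**

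- Paired t test in one arm, n = 30: 0.53 SD of within-arm change.
- Unadjusted two-sample t test on change, 30 per arm (58 degrees of freedom, noncentrality d × √(30/2)): 0.736 SD of between-arm difference. Power is 48% at 0.5 SD and 21% at 0.3 SD.
- ANCOVA: with equal SDs σ and first-visit to week-24 correlation ρ, the variance of change is 2σ²(1 − ρ) and the ANCOVA residual variance is σ²(1 − ρ²). Their ratio is (1 + ρ)/2, so the detectable difference shrinks by √((1 + ρ)/2). For ρ = 0.3, 0.5 and 0.8 this gives 0.736 × 0.806 = 0.593, 0.736 × 0.866 = 0.637 and 0.736 × 0.949 = 0.698. The documents do not give ρ.
- Effect of dropout, for illustration: with 24 completers per arm (assumed), 0.74 becomes 0.83 SD, unadjusted.

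**3. Two components, once between-arm tests are in place.** If success on either component counted and each were tested at 0.05, the family-wise error would be 1 − 0.95² = 0.0975 for independent components, or 0.078 at correlation 0.8. If both must succeed, there is no inflation. These figures describe the repaired plan. As tests of a supplement effect, the within-arm tests in step 1 do not hold 5% in the first place.

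**The case against.** The best defence is that a randomized placebo-controlled design implies a between-arm comparison, and that this brief, roughly translated plan merely failed to write it down. That may be what the sponsor intends. But section 3 does name its tests, and this one is not among them, so it is not prespecified.

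Section 1 might be read as a crossover, with each subject taking six months of each product, which would make a paired test a comparison of treatments. The documents do not support this. Section 3 divides people into two groups, and the schedule ends at week 24, which leaves room for one six-month period only.

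A reader might also infer that the trial measures the wrong disease, or that fat readings will be passed off as steatohepatitis. The text does not bear that out. Section 3 enrols people with non-alcoholic fatty liver disease, section 1 twice pairs fatty liver with fibrosis, and fibrosis matches throughout. Loose wording is the likeliest explanation, so this part is a clarification. Similarly, the instrument is named in section 1, and six months of treatment with a last FibroScan visit at week 24 makes week 24 the natural time point, although no section says so.

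Finally, ANCOVA at week 24 is one sound choice among several, and a between-arm test is less sensitive than the paired test. Both points stand. Neither rescues a within-arm test as evidence against placebo.

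**Conclusion.** The concern holds for the missing between-arm comparison. As written, the plan cannot attribute a change to the supplement. With no supplement effect and a shared improvement of 0.2 to 0.5 SD of change, the supplement arm is significant in 18% to 75% of trials. The supplement arm alone is significant in 15%, 23% and 19% at 0.2, 0.3 and 0.5 SD (at most 25%). These figures rest on 30 per arm, two-sided 0.05, no dropout and an assumed range for the shared improvement. They show a risk, not a certainty of error in this trial.

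It would go too far to say that the trial cannot answer its question: the design and the scheduled measurements support a proper comparison, and only the analysis text lacks it. The open reading, visit, success rule and disease term matter less and are mostly specification.

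**What to change.** In section 3:

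1. Make the primary analysis a between-arm comparison of change from first visit to week 24, adjusted for the first-visit value (ANCOVA if the reading is continuous). Say what follows if the planned normality checks fail. Keep the paired t test as descriptive only.
2. Reconcile steatohepatitis with the fatty liver of section 1, and name one FibroScan reading per component at week 24, the end of the six-month treatment period.
3. State whether success needs both components (each at 0.05) or either one (one designated primary, a fixed sequence, or 0.025 each).

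The documents do not give the trial's status. If it is already unblinded, report these choices as made after unblinding.

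The cost is SAP text, with no new visit or procedure. The price is sensitivity: from 0.53 SD for a within-arm change to 0.74 SD for an unadjusted between-arm difference, or 0.59 to 0.70 SD with ANCOVA if the first-visit to week-24 correlation is 0.3 to 0.8. The sponsor should expect only about 48% unadjusted power at 0.5 SD and 21% at 0.3 SD, and less with dropout.

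### Two primary outcomes and five post-baseline FibroScan visits, but no primary visit, success rule, alpha or multiplicity control, so the primary false-positive rate is not fixed in advance

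*Combined protocol and SAP*

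**What the plan says.** Section 3 (Statistical Analysis Plan) gives one primary end point, which "is to see the severity of changes in the patient's steatohepatitis and fibrosis". It holds two outcomes, and no scale, unit or visit is attached to either. The section plans 60 participants, "divided into two groups, 30 people in each group, double-blind randomized test". The methods it names are normality checks, Pearson correlation and a paired t test: "the Intra-intervention comparison is performed by Paired t test". It names no between-arm test, significance level, sidedness, multiplicity method or testing order.

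Section 1 (Study Protocol) describes "six months of health supplements (experimental group) and six months of placebo (control group" and sets assessments at the first visit and at "4 weeks, 8 weeks, 12 weeks, 16 weeks, and 24 weeks respectively to check blood and biochemical values". In the same sentence it says to "use Fibroscan to detect fatty liver and liver fibrosis". The FibroScan row of the schedule in Section 2 agrees: it is marked at the first visit and at all five later visits, in both arms.

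**The concern.** Two outcomes at five post-baseline visits make ten outcome-by-visit results. The plan does not call for ten primary tests, but nothing in it stops any one of the ten from being reported as the primary result. Outcome, visit and success rule could all be settled after the data are seen. The chance of a false claim is then whatever the eventual choice makes it, and a reader of the report could not tell which rule was in force.

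An alpha rule also needs a valid test to act on. A paired t test within the supplement arm asks whether that arm changed. It does not ask whether it changed more than placebo. Any change shared by both arms, such as natural course, regression to the mean or the effect of taking part in a trial, can make it significant.

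**Working it through.** **Inputs from the documents:** 2 primary outcomes (Section 3), 5 post-baseline FibroScan visits (Sections 1 and 2), 30 per arm (Section 3). The sample size of 60 comes with no alpha, power, effect size or SD, so there is no stated calculation to reproduce.

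**Assumptions:** two-sided 0.05 per test; no effect on either outcome unless stated; tests that are valid for the between-arm difference. The documents give no correlations, so a range is used. Here rv is the correlation between test statistics at different visits, equal for all pairs, and ro is the correlation between the two outcomes.

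**Step 1. Independent tests.** The chance of at least one false positive among k tests is 1 − 0.95^k.
- k = 2 (both outcomes, one visit): 1 − 0.95² = 9.75%
- k = 5 (one outcome, all visits): 1 − 0.95⁵ = 22.6%
- k = 10 (both outcomes, all visits): 1 − 0.95¹⁰ = 40.1%

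**Step 2. Correlated tests.** Multivariate normal simulation, 400,000 replicates, either outcome at any visit:

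| rv | ro = 0 | ro = 0.5 | ro = 0.8 |
|---|---|---|---|
| 0.5 | 33% | 31% | 27% |
| 0.8 | 24% | 22% | 19% |
| 0.95 | 16% | 15% | 13% |

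The rv = 0.5 row has a natural reading. If all raw measurements, baseline included, share one correlation r, two changes from baseline have covariance 1 − r and variance 2(1 − r), so their correlation is 0.5 whatever r is. A separate simulation of t tests on change from baseline with 30 per arm (r from 0.3 to 0.9, ro from 0 to 0.6) gave 30-34%, in line with that row.

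**Step 3. The same data under other success rules** (rv 0.5-0.95, ro 0-0.8):
- Either outcome at week 24 only: 8-10%.
- Both outcomes at week 24: 0.2-2.2%, and at most 5% if one outcome is truly affected.
- Both outcomes, visit chosen freely for each: 0.7-9.5%. If one outcome is truly affected, the error can approach that of testing the other at any visit: 18% (rv 0.5), 13% (0.8) or 8% (0.95).
- Either outcome at week 24 with Holm: 4-5%.

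**Step 4. The paired test, a separate problem.** Suppose both arms change equally by d SD of change, with no treatment effect. The paired t test in the supplement arm has 29 degrees of freedom and noncentrality d√30.
- d = 0.3: noncentrality 1.64, significant 36% of the time.
- d = 0.5: noncentrality 2.74, significant 75% of the time.

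With Holm over two outcomes at week 24, at least one is significant if either p-value is below 0.025. For independent outcomes the single-test rates at 0.025 are 25.2% and 64.7%, so the results are 1 − (1 − 0.252)² = 44% and 1 − (1 − 0.647)² = 88%. At ro = 0.8 they are 34% and 74-75%.

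**Step 5. What control costs.** Two-sample t test, 30 per arm, 80% power, no baseline adjustment. The detectable difference is 0.74 SD at alpha 0.05 and 0.81 SD at 0.025 (the first Holm step). Requiring both outcomes at 0.05 with 80% joint power needs 0.84 SD on each if they are independent (each powered at √0.80 = 89%), falling to 0.80 SD at ro = 0.8.

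**The case against.** The strongest reply is that the plan has a natural reading: one end point, two outcomes joined by 'and', and change over a six-month treatment period. That points to both outcomes at week 24, where the error rate is below 5% and no adjustment is needed. Ten tests is the loosest reading, and the larger percentages describe between-arm tests at 0.05 that the plan never specifies. The link from the primary end point to FibroScan is also an inference: Section 3 does not name the instrument, and Section 1 ties it to fatty liver rather than steatohepatitis.

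Much of this is fair as to size. Ten tests is an upper bound, the percentages are scenarios, and the week 24 figures are the better guide to what a careful analyst would do. But week 24 and 'both' are nowhere written as rules. If week 24 is accepted and either outcome suffices, the rate is still 8-10%. If 'both' is accepted and the visit is left open, it can reach 8-18% when one outcome is truly affected. If a measure other than FibroScan is meant for steatohepatitis, the test count may change, but the missing visit, success rule and alpha do not.

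The paired-test problem is indeed distinct from multiplicity. It is included because a multiplicity rule applied to within-arm tests would give false reassurance.

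**Conclusion.** The concern holds. The SAP fixes no primary visit, either/both rule, alpha or multiplicity control for a two-outcome primary end point measured repeatedly. Uncontrolled here means not fixed in advance: under plausible readings the false-positive rate runs from below 1% to about one in three. These figures rest on an assumed two-sided 0.05, assumed correlations and valid between-arm tests. The conclusion that the rate is left open needs none of those assumptions.

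The absence of a between-arm test is a further defect. At an assumed shared change of 0.3 or 0.5 SD, a single within-arm test misleads 36% or 75% of the time. The point should be settled before unblinding.

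**What to change.** Add to Section 3 wording such as:

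> The primary time point is week 24, the end of the six-month treatment period. The primary analyses are the between-arm differences at week 24 in the FibroScan measure of liver fat and in the FibroScan measure of liver stiffness, each by analysis of covariance with the baseline value as covariate. Family-wise two-sided alpha is 0.05, controlled by Holm's procedure. Results at weeks 4, 8, 12 and 16, and within-arm paired t tests, are supportive.

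Holm makes success mean either outcome, which is for the team to decide. Requiring both at 0.05 each, or a fixed testing order at week 24, is equally valid if chosen before unblinding.

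This wording makes two changes beyond multiplicity. It replaces the within-arm test with a between-arm comparison for the primary analysis. It also replaces steatohepatitis with FibroScan liver fat; if another measure is meant, the SAP should name that instead. Whichever measures are chosen, the SAP should give the scale and unit of each, say whether it is analysed as a continuous value or a grade, and say how missing week 24 values are handled.

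The cost is SAP text only, with no extra visits or measurements. With 30 per arm and 80% power, the detectable difference for the first Holm step rises from 0.74 to 0.81 SD; requiring both outcomes instead needs about 0.80-0.84 SD on each. Baseline adjustment would typically lower these figures when baseline and week 24 values are correlated.

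### The documents describe no record of other medicines, supplements, alcohol or diet programmes, so starts after entry that differ by arm could not be detected or examined

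*Combined protocol and SAP*

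**What the plan says.** Section 3 sets the size: "This study is expected to include a total of 60 people with non-alcoholic fatty liver disease". Allocation is randomised, blinded and equal, at 30 per arm. Section 1 describes six months of supplement against six months of placebo. The primary endpoint "is to see the severity of changes in the patient's steatohepatitis and fibrosis"; FibroScan is the liver measurement scheduled. For the secondary endpoint, "The secondary end point is the degree of change in the patient's weight and lipid profile". Section 1 gives the wider purpose: "to see their effects on fatty liver, liver fibrosis and metabolic indicators".

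The Section 2 table, whose first column is headed "Evaluation Procedure", lists consent, eligibility, two blood panels, HbA1c and FibroScan. It has no row for concomitant medicines, other supplements, alcohol or diet. Section 1 adds phone and monthly-visit reminders with a question about tablet-taking, meant to improve compliance. That question is open-ended, but it names no other item, form or use.

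The only comparison that Section 3 names is a paired t test within each intervention. It names no between-arm test and no variable for other treatment.

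**The concern.** Treatments and habits other than the study tablets can move every outcome here: lipids, weight, glucose markers and liver fat. Alcohol also bears on whether a participant still belongs to a population defined as non-alcoholic.

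The schedule itself produces results that could prompt action. By the Section 2 table, fasting glucose is measured six times over 24 weeks, lipids four times and HbA1c three times. Blinding hides the allocation, but it does not hide an LDL or HbA1c value. If the supplement works, poor values will be more frequent on placebo, and so may be new lipid- or glucose-lowering treatment. Those starts would pull the placebo arm towards the supplement arm and mask a benefit.

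Without records, the report could not say how many people started something else, in which arm or when, and could not test whether the result depends on it. Such histories cannot be reliably rebuilt at analysis.

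**Working it through.** **The plan's own figure.** 30 + 30 = 60, which agrees with Section 3. The sample size cannot be reproduced further, because alpha, power, effect size, SD and dropout are not given.

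**Inputs.** From the documents: 30 per arm, randomised, double-blind, placebo control. Assumed throughout: two-sided alpha of 0.05; an LDL fall of 30 to 40 mg/dL per person who starts a lipid-lowering medicine; an SD of LDL change of 20 to 30 mg/dL; and the uptake rates and effects in SD units given below. No figure in the documents shows how often starts will occur.

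**1. Shift in an arm mean** = extra starts × effect / 30.
- 2 starts: 2 × 30/30 = 2.0 to 2 × 40/30 = 2.7 mg/dL
- 3 starts: 3 × 30/30 = 3.0 to 3 × 40/30 = 4.0 mg/dL
- 5 starts: 5 × 30/30 = 5.0 to 5 × 40/30 = 6.7 mg/dL

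**2. Against the precision of the trial.** Standard error of the between-arm difference = SD × √(2/30).
- SD 20: 20 × 0.258 = 5.2 mg/dL
- SD 30: 30 × 0.258 = 7.7 mg/dL

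Two to three extra starts therefore shift the result by 2.0/7.7 = 0.26 to 4.0/5.2 = 0.77 standard errors. With no supplement effect, that raises false significance from 5% to about 6% to 12%. Five extra starts (5.0/7.7 = 0.65 to 6.7/5.2 = 1.29 standard errors) raise it to about 10% to 25%.

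**3. Background change unrelated to arm** (simulated, 40,000 trials, no supplement effect). If 10% to 30% of both arms start a treatment that moves the outcome by 1 to 1.5 SD:
- the between-arm test is significant in about 5% of trials, as it should be;
- the within-arm paired t test in the supplement arm is significant in about 8% to 50%.

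The SD of the chance imbalance in uptake is √(2q(1−q)/30), which is 8 percentage points at q = 0.1 and 12 at q = 0.3. Multiplied by the effect, it is about 0.08 to 0.18 SD. The standard error of the between-arm test already covers it.

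**4. Uptake that differs by arm** (simulated). At 30 per arm, 80% power by the normal formula needs a difference of (1.96 + 0.84) × √(2/30) = 0.72 SD. Taking 0.72 SD as the true benefit, with more starts on placebo than on supplement:

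| Uptake, supplement vs placebo | Power, 1 SD effect | Power, 1.5 SD effect |
|---|---|---|
| none | 78% | 78% |
| 10% vs 10% | 75% | about 70% |
| 10% vs 20% | 60% | 48% |
| 10% vs 30% | 46% | about 29% |

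The 10% vs 10% row shows that part of the loss is added variance. The further fall comes from the difference in uptake. With no true effect, 10% vs 30% gives false significance of about 11% (1 SD) to 17% (1.5 SD).

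**The case against.** A reader might infer that any change from another cause cannot be told apart from the supplement. The documents do not support that. The trial is randomised, blinded and placebo-controlled, and step 3 shows that a between-arm test holds its 5% level when background change is unrelated to arm, whether or not it is recorded. The inference fits only the within-arm paired t test. That is a gap in the analysis, which records alone would not close.

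A reader might also infer that unequal diet or supplement use would create a false benefit. Under blinding the documents give no reason for such inequality, and chance imbalance is already in the standard error. The mechanism with a stated cause, result-driven starts on placebo, mainly costs power.

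It can further be said that a comparison using all readings, whatever else was taken, is valid without these records. That stands for the question it answers. But the stated aim is the supplement's own effect, and a null result could not then be read as no effect rather than an effect offset by other treatment.

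Finally, it would go too far to say that no such data will exist. The document was not available in full, eligibility criteria are not shown, and the monthly question is open-ended. Entry rules on alcohol or stable medication may exist. They would still not record starts after entry.

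**Conclusion.** The point holds in a limited form. The available text does not describe recording other medicines, supplements, alcohol or diet programmes at baseline or follow-up. Starts after entry that differ by arm could hide a benefit and could not be detected, described or examined.

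The likely distortion is modest. On assumed figures, two or three extra starts move mean LDL by less than one standard error. It becomes serious only with a large gap in uptake, such as 10% against 30%. These calculations cover LDL and a generic outcome in SD units; nothing in the documents allows a specific figure for FibroScan, weight or glucose. The point still merits action because the records are cheap to collect now and hard to recover later.

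**What to change.** 1. **Record.** Add one row to the Section 2 table at First Time and Weeks 4, 8, 12, 16 and 24, covering lipid- and glucose-lowering medicines, other supplements, alcohol intake and any diet or weight-loss programme, with start dates and dose changes.
2. **Name the main analysis first.** In Section 3, specify a between-arm, baseline-adjusted comparison of change at Week 24 that uses all readings regardless of other treatment. Until that is named, there is no between-arm result for a sensitivity analysis to test.
3. **Report and examine.** Tabulate starts and changes by arm. Add one sensitivity analysis of lipids, glucose markers and FibroScan with its rule written down. For example, set readings after a relevant start to missing and multiply impute them from baseline and earlier readings, including those that prompted the start. Simply dropping readings after a result-driven start can itself bias the comparison. Label this analysis supportive.

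Medical care does not change. The cost is a short form taking a few minutes at visits already planned, plus one extra analysis; no new visit or test is needed. If entry rules on alcohol or stable medication exist elsewhere, refer to them in the same place.
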